### **3.1.3 Follow Up Phase**

This phase begins when the decision to discontinue study drug is made. Two follow up visits are required, occurring 35 days  $\pm$  7 days from the last dose (X01) and 80 days  $\pm$  7 days from X01 (X02). Follow up visits include targeted physical examination, laboratory tests, tumor assessments, adverse event and concomitant medication assessments, and PRO instrument collection. Additional details and requirements are outlined in [Table 5.1-4](#). After completion of the first two follow-up visits, subjects will be followed every 3 months for survival, as outlined in [Table 5.1-4](#).

Subjects who discontinue study drug for reasons other than radiographic disease progression will continue to have tumor assessments (if clinically feasible) according to the schedule in [Table 5.1-2](#) and [Table 5.1-3](#) until progression.

Subjects will be followed for drug-related toxicities until these toxicities resolve, return to baseline or are deemed irreversible. All adverse events will be documented for a minimum of 100 days after the last dose of study drug.

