**Stratification factors:**

- Etiology (HCV vs. non-HCV [ie, HBV- and HCC with no history of hepatitis virus infection])
- Vascular invasion &/or extrahepatic spread (present or absent),
- Geography (Asia vs Non-Asia).

**Study Population:** Adult ( $\geq 18$  years) male and female subjects with advanced HCC. Subjects must not be amenable for management with surgery or loco-regional therapy or have progressed after surgery or loco-regional therapy. Surgical and/or locoregional therapy to reduce overall tumor burden prior to study entry is not allowed. Subjects must not have received prior systemic therapy for advanced HCC in keeping with the first-line setting of this study.

Eligibility criteria are defined in the protocol.

**Study Drug: includes both Investigational [Medicinal] Products (IP/IMP) and Non-investigational [Medicinal] Products (Non-IP/Non-IMP) as listed:**

Study Drug for CA209459		
Medication	Potency	IP/Non-IP
Nivolumab Solution for Injection	100 mg (10 mg/mL)	IP
Sorafenib Tablets	200 mg	IP

**Study Assessments:** On treatment visits will occur at Day 1 and every 2 weeks thereafter. Tumor imaging assessments will occur 8 weeks from the date of randomization (+/- 1 wk), then every 8 weeks (+/- 1 wk) thereafter up to 48 weeks, then it will be every 12 weeks (+/- 1 week) until disease progression or treatment is discontinued (whichever occurs later). Subjects will be treated until unacceptable toxicity or disease progression. Following discontinuation of therapy, safety will be assessed through post-treatment Follow Up visit 2 (~ 100 days from last dose). Survival status will be assessed every 3 months after follow up visits are completed, and may be completed via telephone or in person visits.

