### **3 INVESTIGATIONAL PLAN**

#### **3.1 Study Design and Duration**

This is an open-label, two-arm, randomized, Phase 3 study in adult ( $\geq 18$  years) male and female subjects with advanced HCC. Subjects must not be amenable for management with surgery or loco-regional therapy or have progressed after surgery or loco-regional therapy. Subjects must not have received prior systemic therapy for advanced HCC in keeping with the first-line setting of this study.

After screening for eligibility and signing of informed consent, qualified subjects will be randomized in a 1:1 ratio to receive nivolumab or sorafenib. It is expected that approximately 908 subjects will be screened for the study with approximately 726 subjects entering the treatment phase. Approximately 363 subjects will be randomized to each study arm. Stratification will occur

by etiology (HCV vs. non-HCV [ie, HBV- and HCC with no history of hepatitis virus infection]), vascular invasion &/or extrahepatic spread (present or absent), geography (Asia vs Non-Asia).

[figure not shown]
Subjects will receive open-label treatment with one of the following:

- Nivolumab 240 mg IV every 2 weeks until disease progression or unacceptable toxicity
- Sorafenib 400 mg PO BID until disease progression or unacceptable toxicity

On both arms, treatment beyond initial investigator-assessed RECIST 1.1 defined progression is permitted if the subject has investigator assessed clinical benefit and is tolerating study drug, as specified in Section 3.1.6. Specific requirements for subjects treated with nivolumab and sorafenib are described in Sections 4.5.1.6 and 4.5.3.4, respectively.

The study design schematic is presented in Figure 3.1-1.

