Tumor imaging assessment	See Note	See Note	
Tumor imaging assessments during Follow Up and Survival Follow up is required for subjects that have discontinued treatment prior due to reason other than radiologic disease progression.
 
Tumor imaging assessments will occur 8 weeks from the date of randomization (+/- 1 wk), then every 8 weeks (+/- 1 wk) thereafter up to 48 weeks, then it will be every 12 weeks (+/- 1 week) until disease progression.
 
CT of the chest, CT or MRI of abdomen, and pelvis with IV contrast, including required tri-phasic CT of the liver should be performed. CT chest without contrast or MRI abdomen/pelvis is acceptable if CT is contraindicated. Modality (CT or MRI) used at baseline should be used across all imaging timepoints. Bone scan is required if clinically indicated.
 
Subjects with a history of brain metastasis may have surveillance MRI approximately every 12 weeks from the date of first dose, or sooner if clinically indicated

Other Assessments			
PK/IMG sampling	X		To be collected for nivolumab subjects only. See Section 5.5.1

Table 5.1-4: Follow-Up Procedural Outline - all subjects (CA209459)			
Procedure	Follow Up, Visits 1 and 2 (X visits)a	Survival Follow Up Visits (Y visits)b	Notes
Outcomes Research Assessment			The EQ-5D and FACT-Hep should be administered at the start of the visit, before the subject sees the physician and before any study related procedures are done
EQ-5D-3L	X	X	EQ-5D to be assessed during clinical visit or via a phone for survival follow-up visits
FACT-Hep	X	X	FACT-Hep to be assessed during clinical visit or via a phone for survival follow-up visits
Health care resource use (HCRU)	X		Health Care Resource Use (HCRU) to be assessed during clinical visit
Subject Status			
Survival Status		X	Every 3 months after FU 2; may be accomplished by visit or phone contact

a X visits occur as follows: X01 = 35 days ± 7 days from last dose, X02 = 80 days ± 7 days from X01

b S, Survival visits continue every 3 months after X visits

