## **5.4 Efficacy Assessments**

Study evaluations will take place in accordance with the flow charts in [Section 5.1](#). Baseline assessments should be performed within 28 days prior to randomization utilizing CT or MRI. In addition to chest, abdomen, and pelvis, all known sites of disease should be assessed at baseline. Subsequent assessments should include chest, abdomen, and pelvis, and all known sites of disease and should use the same imaging method as was used at baseline. Baseline MRI for brain must be done for known or suspected disease. Subjects will be evaluated for tumor response beginning 8 weeks from the date of randomization (+/-1 wk), then every 8 weeks (+/- 1 wk) thereafter up to 48 weeks, then it will be every 12 weeks (+/- 1 week) until disease progression is documented or treatment is discontinued (whichever occurs later).

Tumor imaging assessments for ongoing study treatment decisions will be completed by the investigator using RECIST (Response Evaluation Criteria in Solid Tumors) 1.1 criteria, see [Appendix 1](#). For a BOR of CR or PR, the initial response assessment must be confirmed by a consecutive assessment no less than 4 weeks (28 days) later. Responders are the subjects with BOR of confirmed CR or confirmed PR. In the case of stable disease (SD), measurements must have met the SD criteria at least once after randomization at a minimum of 7 weeks (49 days). All scans performed for study purposes will be submitted to an imaging core lab for a Blinded Independent Central Review (BICR) supporting primary and secondary efficacy endpoints.

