4.1.2 PFS

[figure not shown]
PFS is defined as the time from the date of randomization to the date of the first objectively documented tumor progression or death due to any cause in all randomized subjects. Subjects who die without a reported prior progression and without initiation of subsequent anti-cancer therapy will be considered to have progressed on the date of their death. Subjects who did not progress or die will be censored on the date of their last tumor assessment prior to subsequent anti-cancer

therapy (if there is any). Subjects who did not have baseline tumor assessment will be censored on the date they were randomized. Subjects who did not have any on study tumor assessments and did not die will be censored on the date they were randomized. Censoring rules for the primary analysis of PFS are summarized in Table 4.1.2-1. Further explanation for various censoring scenarios for the primary definition of PFS are presented in Figure 4.1.2-1.

Table 4.1.2-1: Censoring Scheme used in Primary Analysis of PFS

Situation	Date of Progression or Censoring	Outcome
No baseline tumor assessment	Date of randomization	Censored
No on study tumor assessments and no death	Date of randomization	Censored
Documented progression	Date of the first documented tumor progression	Progressed
No progression and no death	Date of last tumor assessment	Censored
Subsequent anti-cancer therapies started without a prior reported progression	Date of last tumor assessment prior to initiation of the subsequent therapy	Censored
Death without progression and without initiation of subsequent anti-cancer therapy	Date of death	Progressed

[figure not shown]
Figure 4.1.2-1: Graphical display of PFS Primary Definition

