4.3.2 PFS

The secondary endpoint of PFS is the PFS (see [Section 4.1.2](#)) in all randomized subjects with progression is based on the first documented tumor progression assessed by BICR according to RECIST 1.1 or death.

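### PFS counts only BICR progression, but no scans are required after drug is stopped for investigator-called radiographic progression, and no visible PFS analysis tests the effect

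*Protocol*

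**What the plan says.** **Who calls progression.** The protocol describes the trial in 3.1 as follows: "This is an open-label, two-arm, randomized, Phase 3 study". Section 5.4 gives treatment decisions to the site: "Tumor imaging assessments for ongoing study treatment decisions will be completed by the investigator using RECIST" 1.1. Nivolumab stopping (4.5.1.5) and treatment beyond progression in both arms (3.1.6) are tied to the investigator's assessment.

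**When scans are required.**
- On treatment, scans run "until disease progression or treatment is discontinued (whichever occurs later"), per the synopsis and 5.4.
- Off treatment, 3.1.3 says "Subjects who discontinue study drug for reasons other than radiographic disease progression will continue to have tumor assessments (if clinically feasible"), and 3.6 says much the same.
- The imaging note in Table 5.1-4 says follow-up imaging is "required for subjects that have discontinued treatment prior due to reason other than radiologic disease progression".
- Protocol 3.1 adds: "On both arms, treatment beyond initial investigator-assessed RECIST 1.1 defined progression is permitted". Those subjects stay on drug and so stay in the scanning schedule.

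**What PFS counts.** SAP 4.3.2: "progression is based on the first documented tumor progression assessed by BICR according to RECIST 1.1 or death". Under SAP 4.1.2, a subject with neither event is censored at the last tumor assessment. One who starts new therapy first is censored at the "Date of last tumor assessment prior to initiation of the subsequent therapy". A death without progression or new therapy is an event on the date of death, however long after the last scan.

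**Sensitivity analysis.** The one visible in SAP 7.5.3 ignores the start of subsequent therapy. It still takes progression from BICR.

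**The concern.** Blinded central review is meant to shield PFS from open-label judgement. Here the unblinded investigator can decide when the images for that review end. A subject taken off drug at the investigator's call, before BICR agrees, is probably close to a BICR progression that may never be imaged. Censoring that subject is potentially informative, and counting the event at death delays it. A similar subject kept on drug goes on being scanned and can still give a BICR event.

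If the arms differ in how often this happens, PFS can differ between them with no true difference. PFS is a formally tested endpoint with its own alpha allocation (SAP 7.5.4.2), and DOR uses the same censoring scheme. The existing sensitivity analysis can add later deaths and any scans that were done, but it cannot recover progression that was never imaged.

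**Working it through.** **1. The plan's own PFS figures.** SAP 7.5.4.2 expects 704 PFS events at interim and 722 at final, with nominal levels 0.049 and 0.031.
- Information fraction: 704/722 = 0.975.
- Pocock-type Lan-DeMets spending: 0.05 × ln[1 + (e − 1) × 0.975] = 0.0492.
- The final level, solved from the bivariate normal with correlation √0.975, is 0.0307. Both agree with the plan.
- Events among randomized subjects: 722/726 = 99.4%, leaving 726 − 722 = 4 without an event. The forecast makes almost no allowance for lost BICR progressions. It cannot be rebuilt, because the documents give no PFS median.

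**2. Simulation with no true PFS difference.**

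From the documents: 363 subjects per arm, the protocol scan schedule, 13 months of randomization, cut-off at month 33.

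Assumed, not in the documents:
- BICR PFS median 3, 4 or 6 months; OS median 11.4 months, independent of progression; uniform accrual.
- The investigator is one scan ahead of BICR in 10-30% of subjects, and scanning stops there for 40-80% of those.
- 40% of the subjects whose scanning stops start new therapy, except in the last row of the table.

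There were 1,500 trials per scenario, analysed by Cox model and by log-rank test at two-sided 5%. The hazard ratio is nivolumab against sorafenib. Ranges cover the three PFS medians.

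| Subjects lost, sorafenib / nivolumab | Hazard ratio | Rejection rate |
|---|---|---|
| about 4% / 4% | 1.00 | 4.5-5.3% |
| about 12% / 12% | 1.00 | 4.7-4.9% |
| about 8% / 5% | 1.024-1.028 | 6.1-6.9% |
| about 12% / 6% | 1.053-1.058 | 10.9-13.2% |
| about 6% / 12% | 0.943-0.950 | 10.8-13.5% |
| about 12% / 4% | 1.069-1.081 | 15.5-20.7% |
| about 4% / 12% | 0.927-0.935 | 16.3-19.5% |
| about 12% / 6%, new therapy 70% / 30% | 1.034-1.051 | 8.3-10.5% |

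- With scanning continued to BICR progression, the same runs gave hazard ratio 1.00, rejection 4.3-6.5% and 716-725 events. The mild 8%/5% case is therefore barely distinguishable from simulation noise in its rejection rate.
- With equal loss, events fell to 666-709. The smallest drop is 725 − 709 = 16 and the largest 716 − 666 = 50.
- The arm that loses more looks better. When sorafenib loses more, nearly all rejections favour sorafenib. When nivolumab loses more, 10.4-19.3% of trials wrongly favour nivolumab.

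**3. Would the remedy help?** A simpler model was used: exponential PFS with median 4 months, 8-weekly scans, the investigator one scan ahead, scanning ended for every early call, and 50-100% of those subjects starting new therapy.

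| Early calls, sorafenib / nivolumab | Hazard ratio, BICR PFS |
|---|---|
| 10% / 5% | about 1.02-1.03 |
| 30% / 15% | about 1.09-1.10 |
| 15% / 30% | about 0.90-0.93 |

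Counting the investigator's date as the event brought these back to about 0.97-1.03. Some residual shift is expected, because that date precedes the BICR date.

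**The case against.** A reader might infer that all scanning ends at the investigator's call and that the resulting bias differs by arm. The documents support neither.

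- **Scanning does not simply stop.** It runs to the later of progression and end of treatment, and both arms may be treated beyond progression on closely parallel criteria. The gap concerns only subjects who stop drug at the investigator's call and have no BICR progression by then. Their later scans are not required, but they are not forbidden.
- **Some text points to continued imaging.** Protocol 3.1.3 lists tumor assessments among the contents of both follow-up visits. Protocol 4.5.1.5 continues nivolumab assessments after discontinuation, whereas 4.5.3.3 for sorafenib mentions only delay. SAP 4.2 continues imaging until progression. None of these says whose progression is meant, and the Table 5.1-4 note narrows the requirement. This shows inconsistency rather than closing the gap.
- **No arm difference is shown.** The documents give no rate of BICR-investigator discordance or of treatment beyond progression. All the bias in the working comes from assumed imbalance.
- **Unseen material may answer part of this.** The imaging charter could contain a progression-confirmation step. SAP 4.1 lists investigator RECIST 1.1 assessment as a criterion, so a redacted section may already hold an investigator-assessed PFS analysis.
- **Scope is limited.** PFS is tested only if OS and ORR both succeed.

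All five limit the point. None removes the mismatch between the scan rule and the endpoint.

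**Conclusion.** The concern holds as a potential bias in PFS, not a demonstrated one. The scan rule can end the images available to BICR on the investigator's call, and no visible analysis tests the effect. Equal loss costs events but leaves the null comparison at about 1.0. The bias ranges in the working rest wholly on assumed loss rates, so neither size nor direction can be claimed for this trial. The rejection rates describe the PFS test alone at 5%. They are not family-wise error rates, since PFS is reached only after OS and ORR, and the plan's final PFS level is lower (0.031). The primary OS analysis is untouched. This is a worthwhile, inexpensive improvement to a secondary endpoint.

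**What to change.** 1. **Add a supportive PFS analysis to SAP 7.5.3**, unless a redacted section already has one. For subjects without BICR progression whose scanning ended on investigator-assessed RECIST 1.1 progression, count the investigator's progression date as the event. Label it as specified after the lock if it is run on the data locked on 5 June 2019 (SAP 7.10).
2. **Tabulate these subjects by arm** with the PFS censoring-status table in SAP 7.5.3, which has no such category. This would show whether loss was balanced.
3. **Reconcile the imaging text** in Protocol 3.1.3, 3.6, 4.5.1.5, 4.5.3.3 and Table 5.1-4 and in SAP 4.2, so that they agree on whose progression ends imaging.

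The cost is SAP wording, one analysis and one table from data already collected, and a text clarification. The downside is that unblinded investigator dates enter the analysis, so it can support the BICR result but not replace it.

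I would not ask for scanning to be extended to BICR progression. That needs extra scans and BICR results returned during follow-up, and it comes too late for the locked data.

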### **3.1.4 Study Duration**

The duration of the study from start of randomization to final analysis of OS will be approximately 33 months, when the requested number of death events are expected to occur. The study may be stopped earlier for superiority at OS interim analysis. Additional survival follow-up may continue for up to 5 years from the time of this analysis. The study will end once survival follow-up collection has concluded.

### **3.1.5 Review of Safety**

The subjects' safety will be monitored on an ongoing basis as described fully in [Section 6](#). In addition, a BMS medical surveillance team (MST) routinely reviews safety signals across the entire nivolumab program. A Data Monitoring Committee (DMC) will also be established to provide oversight and safety and efficacy considerations in protocol CA209459 (see [Section 7.1](#)).

### **3.1.6 Treatment beyond progression**

Accumulating clinical evidence indicates some subjects treated with immune system stimulating agents may develop disease progression by conventional response criteria before demonstrating clinical objective responses and/or stable disease (see [Section 1.2.6](#)). This phenomenon was observed in the Phase I study of nivolumab, CA209003 and confirmed in multiple phase 3 studies (ie, lung CA209017; melanoma CA209037, CA209066, and CA209067). Two hypotheses explain this phenomenon. First, enhanced inflammation within tumors could lead to an increase in tumor size which would appear as enlarged index lesions and as newly visible small non-index lesions. Over time, both the malignant and inflammatory portions of the mass may then decrease leading to overt signs of clinical improvement. Alternatively, in some individuals, the kinetics of tumor growth may initially outpace anti-tumor immune activity. With sufficient time, the anti-tumor activity will dominate and become clinically apparent.

Similarly there are data to suggest that sorafenib administration beyond first radiological PD could continuously suppress HCC growth and may have survival benefit (See [Section 1.2.6.2](#)).

Therefore, subjects will be allowed to continue study therapy after an initial investigator-assessed RECIST 1.1-defined progression ([Appendix 1](#)) as long as they meet the following criteria:

- Investigator assessed clinical benefit, and
- Subject is tolerating the study drug (nivolumab or sorafenib)

These criteria aim to ensure the risk/benefit for continuing treatment will continue to favor the subjects. The assessment of clinical benefit should take into account whether the subject is clinically deteriorating and unlikely to receive further benefit from continued treatment. Palliative local therapy for isolated lesions may be permitted if the patient is considered to have progressed and is discussed with the BMS Medical Monitor. All decisions to continue treatment beyond initial progression must be discussed with the BMS Medical Monitor and documented in the study records. Subjects will be re-consented with an ICF describing any reasonably foreseeable risks or discomforts.

Subjects should discontinue study therapy upon evidence of further progression, defined as an additional 10% or greater increase in tumor burden from time of initial progression (including all target lesions and new measurable lesions). New lesions are considered measurable if the longest diameter is at least 10 mm (except for pathological lymph nodes, which must have a short axis of at least 15 mm). Any new lesion considered non-measurable may become measurable and therefore included in the tumor burden measurement if the longest diameter increases to at least

10 mm (except for pathological lymph nodes, which must have an increase in short axis to at least 15 mm).

For statistical analyses that include the investigator-assessed progression date, subjects who continue treatment beyond initial investigator-assessed, RECIST 1.1-defined progression will be considered to have investigator-assessed progressive disease at the time of the initial progression event.

### **3.2 Post-Study Access to Therapy**

At the conclusion of the study, subjects who continue to demonstrate clinical benefit will be eligible to receive BMS supplied study drug. Study drug will be provided via an extension of the study, a rollover study requiring approval by responsible health authority and ethics committee or through another mechanism at the discretion of BMS. BMS reserves the right to terminate access to BMS supplied study drug if any of the following occur: a) the marketing application is rejected by responsible health authority; b) the study is terminated due to safety concerns; c) the subject can obtain medication from a government sponsored or private health program; or d) therapeutic alternatives become available in the local market.

